8.2 Statistical analysis of the secondary efficacy variables

All secondary efficacy variables will be summarized for subjects in the FAS.

Unless specified otherwise, both NRI (or MI for continuous variables) and Observed Case analyses will be performed (see Section 8.1.4). No other sensitivity or supportive analyses will be presented for the secondary efficacy variables.

Also, in addition to any endpoint tabulations, summary tables of each endpoint by visit and treatment will be provided.

All p-values presented for secondary efficacy variables will be nominal.

8.2.1 Derivation of IGA response

A static IGA for psoriasis will be used to assess disease severity in all subjects during the study. The Investigator will assess the overall severity of psoriasis using the following five-point scale

(see Table 8–1):

Table 8–1: Five-point Investigator's Global Assessment		
Score	Short Descriptor	Detailed Descriptor
0	Clear	No signs of psoriasis; post-inflammatory hyperpigmentation may be present
1	Almost clear	No thickening; normal to pink coloration; no to minimal focal scaling
2	Mild	Just detectable to mild thickening; pink to light red coloration; predominately fine scaling
3	Moderate Moderate	Clearly distinguishable to moderate thickening; dull to bright red, clearly distinguishable to moderate thickening; moderate scaling
4	Severe 5	Severe thickening with hard edges; bright to deep dark red coloration; severe/coarse scaling covering almost all or all lesions

IGA response is defined as clear [0] or almost clear [1] with at least a two category improvement from Baseline.

All other efficacy variables will be summarized for subjects in the FAS.

All other efficacy variables will be summarized based on imputed data (NRI and MI for binary and continuous variables, respectively) and observed case data (ie, subjects with missing data or who have prematurely discontinued study treatment are treated as missing) unless otherwise specified.

8.3.1 Further analysis of Investigator's Global Assessment

The distribution of the IGA score will be summarized in a shift table comparing the change from Baseline versus post-Baseline by treatment group for the FAS. Cross-tabulations of the Baseline vs post-Baseline IGA score will be reported for each time point, including the number of subjects with missing data.

In addition, the IGA responses as described in Section 8.2.1 will be summarized by treatment group across all visits.

8.3.2 Further analysis of PASI

Absolute value, change from baseline, and percentage change from Baseline in PASI score will be summarized by treatment group and visit.

In addition summaries of the PASI50 response, PASI75 response, PASI90 response and PASI100 response will be summarized by treatment group and visit.

A line plot of the percentage change from Baseline in PASI score over time, by treatment group will be produced.

8.3.3 Analysis of BSA

Absolute value, change from baseline, and percentage change from Baseline in BSA affected by psoriasis will be summarized by treatment group and visit.

8.3.4 Derivation of DLQI score and response

The DLQI questionnaire is used for patients with psoriasis and consists of 10 questions. Question 7 consists of a sub-question which is only to be answered following a "No" response to the main question. The questions are scored as shown below in Table 8–2, and the DLQI score is categorized as shown in Table 8–3.

Table 8–2: DLQI Scoring				
Question Number	0 points	1 point	2 points	3 points
1,2	Not at all	A little	A lot	Very Much
3, 4, 5, 6, 8, 9, 10	Not at all/ Not Relevant	A little	A lot	Very Much
7 yeuse	No – Not at all/ Not Relevant	No – A little	No – A lot	Yes

Table 8-3: DLQI - Categorizat	tion
Category	Score Range
No Effect	0-1
Small Effect	2-5
Moderate Effect	6-10
Very Large Effect	11-20
Extremely Large Effect	21-30

In the case of one missing value the result imputed for that question will be 0 and the DLQI score created as normal. Should two or more questions be unanswered then the DLQI score will be set to missing. For question 7, if "Not relevant" is selected the score for the question will be 0, if the question is answered "No" but the second half of the question is incomplete then the question will still be scored as 0.

A four-point change in the DLQI score has been reported to be meaningful for the subject (within-Subject MCID); while a DLQI absolute score of 0 or 1 indicates no or small impact of the disease on health related QOL.

A line plot of the percentage changes from baseline in DLQI score over time, by treatment group will be produced.

8.3.5 Analysis of DLQI

Absolute value, change from Baseline, and percentage change from Baseline value for DLQI will be summarized by treatment group and visit.

The number and percentage of subjects achieving a DLQI score of 0 or 1 at each visit will be presented by treatment group.

The number and percentage of subjects achieving DLQI MCID (as defined in Section 8.3.4) at each visit will be presented by treatment group.

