#### 9.4 Dermatology Life Quality Index

The DLQI is a questionnaire designed for use in adult subjects with psoriasis. The DLQI is a skin disease-specific questionnaire aimed at the evaluation of how symptoms and treatment affect patients’ health related QOL. This instrument asks subjects about symptoms and feelings, daily activities, leisure, work and school, personal relationships and treatment. It has been shown to be valid and reproducible in psoriasis patients. The DLQI score ranges from 0 to 30 with higher scores indicating lower health related QOL. A 5-point change in the DLQI score (DLQI response) has been reported to be meaningful for the patient (within-patient minimal important difference); while a DLQI absolute score of 0 or 1 indicates no or small impact of the disease on health related QOL. Subjects will be asked to complete the DLQI as outlined in the Schedule of Study Assessments ([Table 5–1](#)). Study site personnel should ensure that each subject completes the instrument prior to leaving the study site.

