1.3 Other efficacy variables

1 other efficacy variables detailed below will be evaluated at all scheduled visits in the Schedule of Assessments (see study). The other efficacy variables detailed below will be evaluated at all scheduled visits in accordance with the Schedule of Assessments (see study protocol Table 5-1). This excludes the primary and secondary variables as specified in Section 2.2.1.1 and Section 2.2.1.2

The other efficacy variables are:

- PASI50, PASI75, PASI90, and PASI100 responsed
- IGA response (Clear or Almost Clear with at least 2 category improvement from Baseline)
- Absolute and percent change from Baseline in PASI score
- Shift from Baseline in IGA score
- Change from Baseline in Dermatology Life Quality Index (DLQI)
- Percentage of subjects achieving a DLQI score of 0 or 1
- Percentage of subjects achieving a minimal clinically important difference (MCID) (improvement from Baseline of four or more) in the DLQI
- Time to PASI50 response
- Time to PASI75 response
- Time to PASI90 response
- Time to PASI100 response
- Absolute and percent change from Baseline in the body surface area (BSA) affected by psoriasis
- Change from Baseline in modified Nail Psoriasis Severity Index (mNAPSI) score (in the subgroup of subjects with psoriatic nail disease at Baseline)
- Change from Baseline in the Subject's Global Assessment of Disease Activity (PGADA) for the arthritis visual analog scale (VAS)
- Change from Baseline in the Psoriasis Scalp Severity Index (PSSI) (in the subgroup of subjects with scalp psoriasis at Baseline)

Confidential Page 9 of 63

- Change from Baseline in Short Form 36 item Health Survey (SF-36) Physical Component Summary (PCS) score, and Mental Component Summary (MCS) score, and individual Variations thereof. domains
- Change from Baseline in the Subject Symptom Diary responses (for subjects at sites in selected countries)
- Patient Global Impression of Change (PGIC)
- Change from Baseline in Patient Global Impression of Severity (PGIS)
- Change from Baseline in Hospital Anxiety and Depression Scale (HADS) HADS-A and HADS-D scores
- Percentage of subjects with scores below eight in HADS-A and HADS-D (subjects with normal scores)

2.2.2

2.2.2.1

The PK variables are:

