3.5.2 Randomized Set

The Randomized Set (RS) will consist of all randomized subjects.

Full Analysis Set

The FAS will consist of all randomized subjects who received at least one dose of the study medication and have a valid measurement of the primary efficacy variable at Baseline.

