8.3.11 Analysis of PSSI

The analysis of PSSI score will be conducted for subjects who have scalp psoriasis, defined as PSSI>0 at Baseline.

The change from Baseline will be summarized at each visit by treatment group.

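### DLQI MCID response is reported on the whole FAS, where a subject whose Baseline DLQI is below the threshold cannot respond (minor; descriptive variable)

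*SAP*

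**What the plan says.** - **Planned output.** SAP 8.3.5 presents, at each visit and by treatment group: "The number and percentage of subjects achieving DLQI MCID (as defined in Section 8.3.4").
- **Response rule.** SAP 2.2.1.3 defines DLQI MCID response as "improvement from Baseline of four or more". SAP 8.3.4 gives the basis: "A four-point change in the DLQI score has been reported to be meaningful for the subject". Protocol 4.1.3 and 9.4 use 5 points instead, and SAP 3.11, which lists departures from the protocol's analyses, does not mention the change.
- **Analysis set.** SAP 8.3 states: "All other efficacy variables will be summarized for subjects in the FAS". Binary variables are shown with non-responder imputation and as observed cases. Neither SAP 8.3.4 nor 8.3.5 sets a minimum Baseline DLQI.
- **Who is in the FAS.** Subjects need at least one dose and must "have a valid measurement of the primary efficacy variable at Baseline", which concerns PASI, not DLQI. The severity criteria in protocol 6.1 are PASI, BSA and IGA.
- **Scale.** Protocol 9.4: "The DLQI score ranges from 0 to 30", with higher scores worse.
- **Other DLQI outputs.** SAP 8.3.5 also reports absolute value, change, percentage change and the proportion scoring 0 or 1. SAP 6.2 summarizes Baseline DLQI as a continuous variable only.
- **Restricted variables.** SAP 8.3.7 limits the nail score to subjects with nail disease at Baseline. SAP 8.3.11 does likewise for the scalp: "The analysis of PSSI score will be conducted for subjects who have scalp psoriasis".

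**The concern.** The largest improvement a subject can show equals the Baseline score. A subject who enters at 3 and ends at 0 has lost all measured impact of the disease and counts as a success in the DLQI 0/1 table, yet is a failure in the MCID table. The observed-case version does not help, because such a subject has observed data and still cannot respond.

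Low Baseline scores are possible under the SAP's own scoring. Table 8-3 has categories for 0-1 and 2-5, and SAP 8.3.4 scores as 0 a single unanswered question, a not-relevant answer and an incomplete question 7.

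At stake is how the responder table reads. Its rate would be capped below 100%, and the contrast with placebo would look smaller than it is among subjects who could respond. No planned table shows how many subjects per arm this concerns, so a reader of the tables could not correct for it.

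**Working it through.** **The plan's own figure.** Neither document gives a DLQI responder rate, a Baseline DLQI distribution or a power figure for this variable. The only power figure is above 99% for the PASI90 trend (protocol 14.8, SAP 2.4). It reproduces. With scores -2 to 2, rates 2%, 20%, 40%, 50%, 60% and 40 per arm:

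- T = 40 x (-0.04 - 0.20 + 0 + 0.50 + 1.20) = 58.4
- null variance = 40 x 0.344 x 0.656 x 10 = 90.27
- alternative variance = 40 x (4 x 0.0196 + 0.16 + 0 + 0.25 + 4 x 0.24) = 57.94
- z = (58.4 - 1.96 x 9.50)/7.61 = 5.23, so power exceeds 99.99%

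This has no bearing on the DLQI point.

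**Inputs.** From the documents: 40 subjects per arm, six arms, DLQI floor 0, threshold 4 (SAP) or 5 (protocol). Assumed: share f below the threshold, 0 to 20%; response among subjects able to respond, 90% active and 30% placebo.

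**Step 1, dilution.** FAS rate = (1-f) x p, so FAS difference = (1-f) x (0.90 - 0.30).

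**Step 2, chance imbalance.** The SD that random variation in f contributes to a difference between two arms is sqrt((p1^2 + p2^2) x f(1-f)/40). For two active arms this is 0.9 x sqrt(2f(1-f)/40). For active versus placebo it is sqrt((0.81 + 0.09) x f(1-f)/40).

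| f | Unable to respond, per 40 | FAS rates | Difference (points) | Imbalance SD, two active arms | Imbalance SD, active vs placebo |
|---|---|---|---|---|---|
| 0 | 0 | 90% vs 30% | 60 | 0 | 0 |
| 5% | 2 | 85.5% vs 28.5% | 57 | 4.4 | 3.3 |
| 10% | 4 | 81% vs 27% | 54 | 6.0 | 4.5 |
| 20% | 8 | 72% vs 24% | 48 | 8.0 | 6.0 |

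**Step 3, presence in each arm.** The chance that an arm of 40 has at least one such subject is 1-(1-f)^40. At f = 5% this is 87%, and for all six arms 0.871^6 = 44%. At f = 10% the figures are 98.5% and 92%.

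**Step 4, precision of the restricted table.** The imbalance in Step 2 is part of the ordinary binomial SD of the FAS difference, not an addition to it. At f = 10%:

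- Two active arms: FAS sqrt(2 x 0.81 x 0.19/40) = 8.8 points; restricted, 36 per arm, sqrt(2 x 0.90 x 0.10/36) = 7.1 points.
- Active versus placebo: FAS sqrt((0.81 x 0.19 + 0.27 x 0.73)/40) = 9.4 points; restricted sqrt((0.09 + 0.21)/36) = 9.1 points.

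For two active arms the corresponding pairs are 7.9 and 6.9 points at f = 5%, and 10.0 and 7.5 points at f = 20%. The smaller denominator costs no precision under these assumptions.

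**The case against.** **The FAS denominator answers a legitimate question**, namely what share of treated subjects gained a meaningful improvement. The protocol defines the variable as a percentage of subjects with no subgroup, and the SAP follows it. This stands, and is why the full-FAS table should stay.

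**Other outputs cover much of the ground.** Mean change and DLQI 0/1 are reported in the FAS, and a low-Baseline subject who clears succeeds on 0/1. Baseline DLQI is summarized by arm with mean, SD, median and range, and Baseline characteristics are listed by subject, so gross imbalance would be visible. This stands in part: the number below the threshold in each arm is still not tabulated.

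**The consequence is small.** The variable is in the third tier of efficacy variables, with frequency tables, no test and no place in the testing sequence. This stands and sets the priority.

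**A reader might infer that the SAP breaks its own rule**, since nail and scalp scores are restricted at Baseline. The documents do not support that. Those are organ-specific populations named in the objectives and variable definitions, and they apply to change scores. Elsewhere the SAP keeps everyone: the HADS below-8 summary includes subjects already normal at Baseline, and PGADA is summarized for all subjects with the arthritis subset shown separately.

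**Conclusion.** The mechanism is certain from the documents: any subject below the threshold at Baseline cannot respond, nothing excludes such subjects, and they stay in the denominator. The size is conditional. Rates and differences shrink by (1-f), which on the assumed 90% and 30% takes 60 points to between 57 and 48 for f of 5% to 20%. Chance imbalance contributes an SD of 4.4 to 8.0 points between two active arms and 3.3 to 6.0 points for active versus placebo.

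Two stronger readings should be resisted. A reader might infer that part of every arm is bound to fail. The documents contain no Baseline DLQI distribution, so f could be zero, and at f = 5% all six arms would contain such a subject in only 44% of trials. A reader might also infer biased comparisons between doses. Randomization makes the expected share equal across arms, so the systematic effect is attenuation; the imbalance is sampling variation in a table that carries no test.

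This is a minor, inexpensive improvement. The primary and secondary analyses and the sample size are untouched.

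**What to change.** 1. Reconcile the MCID threshold between protocol 4.1.3 and 9.4 (5 points) and SAP 2.2.1.3 and 8.3.4 (4 points), and record the outcome in SAP 3.11. The Baseline cut depends on it.
2. In SAP 8.3.5, add DLQI MCID response among FAS subjects whose Baseline DLQI is at or above the agreed threshold, and show that denominator by arm.
3. Keep the full-FAS MCID table alongside it, so the protocol's variable is still reported. Leave mean change and DLQI 0/1 in the full FAS.

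The cost is one sentence, one subset flag and one more table, with a denominator smaller by 2 to 8 subjects per arm at f of 5% to 20%. The flag uses only a Baseline value, so the comparison remains between randomized groups.

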8.3.6 Derivation of mNAPSI score

Psoriatic nail disease will be evaluated at the Baseline visit using the mNAPSI. All affected nails will be scored (0 to 3) for onycholysis/oil drop dyschromia, nail plate crumbling, and pitting and will be scored (0 for "no" or 1 for "yes") for leukonychia, nail bed hyperkeratosis, splinter haemorrhages and red spots in the lunula. The score for an individual nail ranges from 0 to 13 with higher scores indicative of more severe nail disease. The total mNAPSI score is the sum of the scores for each individual nail. If a nail is unaffected, it will be recorded as such and will not contribute to the total mNAPSI score. Subjects with nail disease at Baseline are defined as those with a mNAPSI score >0 at Baseline.

If 1 or 2 response items scored on the 0 to 1 scale are missing, the missing response(s) will be imputed by the average of the available responses. Otherwise, the total mNAPSI score will be set to missing.

8.3.7 Analysis of mNAPSI

The change from Baseline in mNAPSI scores will be summarized at each visit by treatment group for the subset of subjects with psoriatic nail disease at Baseline.

The rGADA for the arthritis VAS will be used to provide an overall evaluation of arthritis disease symptoms. Subjects will respond to the question, "Considering all the ways your arthritis affects you, please mark a vertical line on the scale below to show how you are feeling today."

8.3.9

8.3.9 Analysis of PGADA for the arthritis VAS

The actual and change from Baseline in PGADA VAS scores will be summarized at each visit by treatment group.

Subjects who have psoriatic arthritis as defined by the Toronto Psoriatic Arthritis Screening questionnaire (ToPAS) questionnaire results at the baseline assessment will also have the PGADA VAS scores summarized separately.

8.3.10 **Derivation of PSSI**

The PSSI considers both the extent of the scalp area of involvement and the severity based on the scoring scales outlined in Table 8–4 and Table 8–5

The assessment considers erythema, induration and desquamation on the scalp. For each of these three elements, the scores of the area and severity are multiplied. Then, the score from each element is totaled to obtain the PSSI score As with the PASI, the PSSI score ranges from 0 to 72 with a higher score indicating increased scalp disease severity.

If a subject is missing 1 severity measurement, the average of the remaining severity measurements will be utilized to substitute for the missing severity measurement. If the area of affected skin is missing or if 2 or more severity measurements are missing, then the PSSI score will be set to missing.

Table 8–4: PSSI assessment of extent of scalp psoriasis			
Score	Definition		
1 , , , ,	<10%		
2	10-29%		
3	30-49%		
4	50-69%		
5	70-89%		
6 6	90-100%		

Table 8–5: PSSI assessment of clinical symptoms		
Score	Definition	
0	Absent	
1	Slight	
2	Moderate	
3	Severe	
4	Severest possible	

8.3.11 Analysis of PSSI

The analysis of PSSI score will be conducted for subjects who have scalp psoriasis, defined as PSSI>0 at Baseline.

The change from Baseline will be summarized at each visit by treatment group.

8.3.12 Derivation of SF-36

The SF-36v2, standard recall, measures the following 8 health domains as rated by the subjects over the past four weeks: Physical Functioning, Role Physical, Bodily Pain, General Health, Vitality, Social Functioning, Role Emotional, and Mental Health. The classification of the questionnaire items to the health domains is shown in Section 12.1.

The SF-36 Physical and Mental Component Summary scores (PCS and MCS, respectively) are used to measure the two broad components, or aspects, of health-physical and mental. PCS and MCS are based on the aggregate of 8 health concepts described above and all of the 8 health domain scales are used to score both components summary measures.

One additional item asks respondents about health change over the past year.

The SF-36 will be used using QualityMetric's Health Outcomes[™] Scoring Software. The software uses updates 2009 U.S. population norms and applies a Full Missing Score Estimation (Full MSE) method as follows:

- A health domain score (except the PF domain) will be estimated provided that at least one non-missing response is available within that domain
- For the PF domain item response theory will be used to develop a model for estimates of the missing score

Regression methods are then applied to estimate the PCS and the MCS on the basis of the available domains.

8.3.13 Analysis of SF-36

The change from Baseline in the SF-36 PCS and MCS scores as well as for the individual domain scores will be summarized at each visit by treatment group.

Confidential Page 36 of 63

As a sensitivity analysis the SF-36 PCS, MCS and individual domain scores will be also summarized at each visit and by treatment group for the complete cases, where any missing data or variations thereof will result in the affected domains and component scores for that visit also being set to missing.

8.3.14 **Definition of Time to PASI Response**

Time to PASI50, PASI75, PASI90, and PASI100 response (in days) will each be calculated as:

Date of first PASIx response – Date of Baseline visit +1

8.3.15 **Analysis of Time to PASI Response**

Time to PASI50, PASI75, PASI90, and PASI100 response will each be estimated and presented using the Kaplan-Meier product-limit method for each treatment group.

Kaplan-Meier plots of time to PASI50, PASI75, PASI90, and PASI100 response will be presented by treatment group.

Subjects who discontinue study treatment prior to achieving a response will be censored at the date of study treatment discontinuation. Subjects who reach the Week 12 Visit without achieving the given response will be censored at the date of the Week 12 Visit.

The median time to response, including the two-sided 95% confidence interval, will be calculated for each treatment. Comparisons of each bimekizumab dose vs placebo will be analyzed using a log-rank test stratified by region and prior biologic exposure. In addition between group differences for bimekizumab 320mg loading dose + 160mg O4W vs bimekizumab 160mg Q4W and bimekizumab 320mg loading dose + 160mg Q4W vs bimekizumab 320mg Q4W will be analyzed using the log-rank test stratified by region and prior biologic exposure.

Definition of Subject Symptom Diary responses 8.3.16

UCB is developing a new PRO measure that will be used to assess key symptoms relevant to subjects with moderate to severe chronic plaque psoriasis.

PS0010 will use the draft PRO measure in selected countries to enable psychometric validation of the PRO. Site staff will train the participating subjects on the use of the electronic PRO (ePRO) diary at the Screening visit, following which the device will be dispensed to the subject for home use until the Week 12 Visit.

The ePRO diary will be administered on a daily basis from Baseline to the Week 12 Visit. Item content of the ePRO diary will be finalized prior to study initiation and will include a variety of psoriasis-related characteristics, reported as relevant by subjects in the published literature and planned concept elicitation interviews.

The ePRO diary will also administer appropriate anchor items (eg., subject global impression of change, and subject global impression of concept) at the end of every study week.

The weekly score is the sum of the individual scores within the week. A maximum of 3 missed days are permitted (irrespective of whether these are consecutive or not) for the derivation of the weekly score and will be included in the analysis. The missing days will be counted as missing data for the purposes of the weekly score.

13 June 2017 PS0010

8.3.17 **Analysis of Subject Symptom Diary responses**

The mean responses for each question on the subject symptom diary will be summarized by treatment group and week, in terms of absolute values and changes from baseline.

The HADS was chosen for its well-established psychometric properties and its use in clinical research on biological therapy in subjects with chronic plaque psoriasis (Snaith et al, 1994). The HADS scores for anxiety and for depression range from 0 to 21 with higher scores indicating worse state. A score below 8 is considered to be normal a score. considered severe (Langley et al, 2009).

8.3.19 **Analysis of HADS**

Change from Baseline in HADS-A and HADS-D will be summarized at each visit by treatment group.

In addition the percentage of subjects with scores below 8, between 8 and 10, between 11 and 14 and greater than 14 in HADS-A and HADS-D will be summarized by visit and treatment group.

8.3.20 **Definition of PGIC**

The PGIC will be assessed at Baseline and on a weekly basis following the completion of all the patient symptom diary items. Only subjects in selected countries who participate in the completion of the patient symptom diary will participate in the completion of the PGIC.

The PGIC is a five-item instrument that will ask the participants to think about their psoriasis related symptoms (including itching, pain, scaling, and sleep loss) since they started this study. Each item has seven response categories ranging from "Very much improved," "Much improved," "Minimally improved," "No change," "Minimally worse," "Much worse," to "Very much worse."

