Unless otherwise specified, the last valid measurement before study medication administration in the double-blind period will be used as the Baseline value. The same Baseline definition will used for the follow-up period. If a Baseline visit measurement is available the contraction of the same baseline definition will be used as the Baseline value.

Baseline assessment is taken on the same day as first administration of study medication and no time is collected, it will be assumed to have been taken prior to study medication?

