4.2.3 Handling missing data for other efficacy variables

For the dose/exposure response model, missing data will not be imputed. If a subject drops out, this will be used as a covariate in the model. However, the dose/exposure response model is outside of the scope of this SAP and is described in greater detail in a separate data analysis plan (DAP).

Other categorical efficacy variables will be imputed using NRI (ie. Missing data or subjects who prematurely discontinue study treatment prior to Week 12 will be counted as non-responders) or summarized as observed cases. One exception to this rule is the imputation of missing data when summarizing HADS-A and HADS-D scores below 8 (ie. Normal HADS scores). In these summaries, LOCF will be used. That is, the last available HADS-A/HADS-D score while the subject was on study treatment will be carried forward to the missing time points to determine whether or not the subject had normal HADS scores.

Continuous efficacy variables will be imputed using multiple imputation (MI) via the Markov-Chain Monte Carlo (MCMC) method. Summaries based on observed case data will also be prepared.

The MI procedure for continuous efficacy variables (based on MCMC) will be applied as follows using a starting "seed" value of 17402:

Confidential Page 18 of 63

- 1. Create a dataset, one for each treatment group, of subjects with observed values and those needing estimation by multiple imputation. The missing values in each dataset will be filled in using the MCMC method with a total of 100 sets of imputations being performed. Biologic exposure, geographic region and values at baseline and at each post-baseline visit (in chronological order) will be included in the imputation model. If required, in order to facilitate the imputation model, variables can be omitted in the order of biologic exposure and geographical region. Cut-off values will be applied to the imputed data, as appropriate, to ensure that imputed values do not exceed the range of plausible values for the variable being imputed. The resulting datasets for each treatment arm will be combined into one complete dataset based on each of the 100 imputations
- 2. The relevant change from Baseline (or percent change from Baseline) values will then be derived based on the datasets which include observed and imputed values for the variable being considered

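### The diary weekly score (SAP 8.3.16) is an unrescaled sum that accepts up to three missed days, and SAP 8.3.17 does not say whether that sum or a daily mean is analysed

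*SAP*

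**What the plan says.** Change from Baseline in the diary responses is one of the other efficacy variables (protocol 4.1.3, SAP 2.2.1.3), collected at sites in selected countries.

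- **Weekly score, SAP 8.3.16.** "The weekly score is the sum of the individual scores within the week". On incomplete weeks: "A maximum of 3 missed days are permitted", whether consecutive or not, "for the derivation of the weekly score and will be included in the analysis". Then: "The missing days will be counted as missing data for the purposes of the weekly score". No averaging, proration or within-week imputation is given.
- **Analysis, SAP 8.3.17.** "The mean responses for each question on the subject symptom diary will be summarized by" treatment group and week, as absolute values and as changes from Baseline. The weekly score is not named.
- **Missing data, SAP 4.2.3.** Continuous efficacy variables are multiply imputed, and "values at baseline and at each post-baseline visit (in chronological order) will be included in the imputation model".
- **Baseline.** The only rule is the general one in SAP Section 3 (between 3.1 and 3.3): "the last valid measurement before study medication administration". No diary-specific or weekly Baseline is defined. Protocol 8.2 lists diary responses among the pre-dose procedures at the Baseline Visit.
- **Diary start.** SAP 8.3.16: "The ePRO diary will be administered on a daily basis from Baseline to the Week 12 Visit". Protocol 9.11 has daily completion starting at Screening.

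**The concern.** A sum over fewer days is smaller even when symptoms have not moved. If weeks with four, five or six entries are kept and summed without rescaling, the score measures diary completion as well as symptoms. The documents do not give the direction of the draft scale. If higher means worse, missed entries look like improvement.

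The sentence that treats missed days as missing data does not remove the difficulty. It cannot make the whole week missing, because the sentence before it retains such weeks, and it does not call for an average. Elsewhere the SAP does write out average substitution when it wants it: for PASI (8.1.1), mNAPSI (8.3.6) and PSSI (8.3.10). A programmer who follows 8.3.16 as written has no instruction to prorate.

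At stake is the interpretability of the diary summaries in a study that uses the draft instrument for psychometric validation. No formal test depends on them.

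**Working it through.** The plan gives no numerical figure for the diary, so there is none to reproduce. The check is arithmetic on the stated rule.

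**Inputs.** Seven diary days per week (daily completion, protocol 9.11 and SAP 8.3.16). At most three missed days, so k = 7, 6, 5 or 4 days observed (SAP 8.3.16). Constant daily score s (assumed, to isolate the artefact).

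**Step 1: level of a retained week.** The sum is k·s against 7·s for a full week, so the error is k/7 − 1.

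- k = 6: 6/7 − 1 = −14.3%
- k = 5: 5/7 − 1 = −28.6%
- k = 4: 4/7 − 1 = −42.9%

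**Step 2: does the imputation repair it?** The model in SAP 4.2.3 takes Baseline and post-baseline visit values, not daily entries. A week with four to six entries already has a score, so it enters as an observed value and is left as it is.

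**Step 3: rescaling.** The mean of available days is k·s/k = s. The prorated sum is k·s × 7/k = 7·s, with factors 7/6 = 1.167, 7/5 = 1.400 and 7/4 = 1.750. The error is 0% for every k.

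**Step 4: average size under assumed completion.** The documents give no completion rate. Assume days are completed independently with probability p, so k ~ Binomial(7, p), and condition on k ≥ 4:

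| p (assumed) | retained weeks with at least one missed day | average shortfall, E[k given k ≥ 4]/7 − 1 | weeks with k < 4 |
|---|---|---|---|
| 0.95 | 30.2% | −5.0% | 0.02% |
| 0.90 | 52.0% | −9.9% | 0.27% |
| 0.80 | 78.3% | −18.6% | 3.33% |

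**Step 5: what this does to change from Baseline.** Suppose Baseline is also a weekly sum, with average observed fractions c0 at Baseline and c1 later, unrelated to the score. With constant symptoms, expected change is 7·s·(c1 − c0).

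- If c1 = c0, expected change is zero. A real change is attenuated by the common factor but none is created.
- If completion moves from 95% to 80%, the fractions are 0.9501 and 0.8136. The apparent mean change is 0.8136/0.9501 − 1 = −14.4%.
- For arms with the same symptom level, a spurious difference in mean change needs c1 − c0 to differ by arm.

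**Step 6: single-day Baseline.** If the general rule picks one daily entry s and the later value is a weekly sum, an unchanged subject has k·s, that is 4 to 7 times Baseline. This shows only that the scales do not match. It does not predict any output.

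**The case against.** The strongest reply is that no planned table is shown to use the sum. SAP 8.3.17 is the only diary analysis, and it specifies a mean for each question. Read as the mean of a subject's completed days, it is free of the error. This stands, and it makes the bias conditional. It does not close the point: 8.3.16 says that weeks with missed days go into the analysis, and the mean in 8.3.17 could equally be a group mean of weekly sums.

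It can also be said that missing is not the same as zero, and that the individual scores summed could be items, days or both. That is fair as a comment on loose wording. But a sum over the entries present gives the same number as adding zeros, and no other computation is written.

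A reader might infer that the diary results will show false improvement of up to 42.9%. The documents do not support that. The percentages in Step 1 describe the level of one retained week. They become a change from Baseline only against a complete Baseline week, and no weekly Baseline is defined. The average shortfalls in Step 4 are likewise not false change in themselves: completion must also shift over time, and for arm comparisons that shift must differ by arm.

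On Baseline, the general rule does supply a default, and protocol 8.2 schedules a pre-dose diary response. On a daily-mean scale that value is usable. The mismatch arises only if the sum is analysed.

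**Conclusion.** The weekly score as written is wrong for incomplete weeks, by 14.3%, 28.6% or 42.9% for 1, 2 or 3 missed days at constant daily symptoms, and the imputation does not correct it. Whether this reaches the reported summaries depends on a choice that SAP 8.3.17 leaves open. With a mean over completed days there is no error. With the sum, mean change from Baseline is biased when completion differs between Baseline and later weeks, and a single-day Baseline is on the wrong scale. The average shortfalls of 5.0% to 18.6% rest on assumed completion of 95% to 80% with independent days.

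The differing diary start is a separate inconsistency. The device is handed out at Screening, but the documents do not settle whether a full pre-dose week of entries exists.

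The impact is minor. The variable is descriptive, comes from a draft instrument and is collected in selected countries. The primary and secondary endpoints, the type I error control and the sample size are untouched.

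**What to change.** - In SAP 8.3.16, define the weekly value per item as the mean of the available daily scores, or equivalently the sum × 7/days observed, when at least 4 of 7 days are present; otherwise missing. This keeps the SAP's own limit of three missed days.
- In SAP 8.3.17, state that this is the value summarized.
- Put Baseline on the same daily-mean scale: use the pre-dose diary days if they were collected, and otherwise the pre-dose value under the general Baseline rule.
- Reconcile the diary start between protocol 9.11 (Screening) and SAP 8.3.16 (Baseline).

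The cost is a few sentences in the SAP and one line in the derivation program. No new data are needed. Under the completion rates assumed above, the 4-of-7 rule sets 0.02% to 3.33% of weeks to missing, which the existing tolerance would already exclude.
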